8. STUDY ASSESSMENTS AND PROCEDURES

All patients will undergo baseline liver mass protocol abdominal MRI without and with contrast within 30 days prior to the shunt study, and 1, 3, 6, and 12 months after Y90 RE therapy.

Objective TR will be evaluated longitudinally using mRECIST criteria by [name] with a help of an abdominal radiologist. TDR will be calculated using two different methods: 1. Mean dose of the entire tumor resulting in objective TR; 2. Determination of % tumor volume receiving >100 Gy resulting in objective TR. The reason for the second TDR calculation is to take into account the non-homogeneity of Y90 dose delivered to the tumors previously reported.[27, 28] TDR threshold based on logistic regression will be determined by Drs. [name] and [name].

Additional scan assessments may be collected based on clinical symptoms, as appropriate. Documented tumor measurements are required using CT scans, MRI, physical examination, and/or digital photography, as appropriate. Any imaging used to assess disease at any time point will be submitted for an independent radiology review. The same method of assessment (CT or MRI and/or digital photography) and the same technique for acquisition of images must be used for all

study assessments (contrast must be used unless medically contraindicated). Baseline imaging should be done at the same institution/facility which will be used to measure response during the patient's participation in the study. Radiographic assessments and efficacy analyses will be conducted by the Investigator site as well as the independent radiology review committee.

8.1 Schedule of study procedures

Before study entry, throughout the study, and following study drug discontinuation, various clinical and diagnostic laboratory evaluations are outlined. The purpose of obtaining these detailed measurements is to ensure adequate **safety and tolerability assessments**. Clinical evaluations and laboratory studies may be repeated more frequently if clinically indicated. The Schedules of Assessments during the screening and treatment period is provided following the Protocol Synopsis.

Screening Phase

Screening procedures will be performed up to 14 days prior to enrollment and initiation of Y90 therapy as applicable, except for baseline imaging (up to 28 days allowed) unless otherwise specified. All subjects must first read, understand, and sign the IRB/REB/IEC-approved ICF before any study-specific screening procedures are performed. After signing the ICF, completing all screening procedures, and being deemed eligible for entry, subjects will be enrolled in the study. Procedures that are performed prior to the signing of the ICF and are considered standard of care may be used as screening assessments if they fall within the screening window.

The following procedures will be performed during the **Screening Visit**:

- Informed Consent
- Review of eligibility criteria
- Medical history and demographics
- Complete physical exam
- ECOG Performance Status
- Vitals signs, weight and height
- Review of prior/concomitant medications
- Imaging by CT/MRI
- Clinical laboratory tests for:
 - Hematology
 - Complete Metabolic Panel (CMP)
 - Coagulation (PT, PTT, INR)
 - Creatinine Clearance
 - Serum or urine pregnancy test (for women of childbearing potential)

Treatment Phase

Procedures to be conducted during the treatment phase of the study are presented in the Schedule of Assessments (Section 1.3). Screening procedures performed within 7 days of mapping do not need to be repeated on mapping day.

A. Pre-procedure evaluation on Mapping day (Monday)

- Brief medical history
- Symptom-directed physical exam
- ECOG Performance Status
- Vitals signs
- Review of prior/concomitant medications
- Clinical laboratory tests for:
 - Hematology
 - CMP
 - Serum pregnancy test (for women of childbearing potential)

B. 1st Mapping Angiography and Administration of ^{99m}Tc MAA (Monday)

The shunt studies will be performed by [name] on Mondays for reasons explained below. Radial or femoral arterial access will be obtained. A 5 Fr catheter will be used to select superior mesenteric artery and celiac trunk. A 2.8 Fr microcatheter will be advanced to the right or left hepatic artery branch supplying the targeted HCC lesion(s). From this location, detailed evaluation of hepatic arterial vasculature using conventional angiography and 3D cone beam CT (CBCT) will be performed to ensure complete perfusion of the targeted tumor(s) and absence of visible non-target embolization. If a potential non-target vessel (i.e. gastroduodenal or right gastric artery) is observed, the vessel will be embolized using coils. From the catheter location where CBCT was performed, 4 mCi of Tc^{99m} MAA will be administered. **The catheters will be removed, and the arterial access sheath will be secured in place. This is commonly done for our out of town or out of country patients at Emory in whom both mapping and Y90 is performed on the same day. Before the patient leaves the IR suite, all the catheters will be removed. The sheath is gently sutured to the overlying skin. Multiple tegaderms will be applied. Additionally, for the radial access cases, an arm-board will be applied. When taking all the pre-cautions detailed above, we have not experienced any accidental dislodgment during patient transport/waiting.** The patient will be then transferred to nuclear medicine department for ^{99m}Tc MAA planar and SPECT/CT of the chest and abdomen.

C. ^{99m}Tc MAA Planar and SPECT/CT of chest and abdomen (Monday)

Planar and SPECT/CT of chest and abdomen will be obtained with low energy filter according to our standard clinical protocol at Emory. The patient will be then transferred back to IR for 2nd mapping angiography and administration of low-dose Y90. **Quantitative reconstruction of SPECT/CT with Tc-99m is available with MIM Software[40].**

D. 2nd Mapping Angiography and Administration of low dose Y90 (Monday)

Fifteen (15) mCi of resin microsphere will be drawn from a 5-day flex dose vial containing approximately 196 mCi of activity. [name] will oversee the extraction of the low dose by nuclear medicine technologists. The patient will be brought back to IR on the same day (Monday). Using the technique detailed above, the same hepatic artery branches where MAA injection was performed will be selected. From this location, 15 mCi of resin Y90 microspheres will be administered. **After the procedure, patient's femoral sheath will be removed and hemostasis will be achieved with manual compression or closure device. If procedure performed via radial access, which is more commonly performed currently at Emory, the radial sheath will stay in and removed according to IR protocol after Y90 SPECT/CT.**

The remainder of the activity will be used for therapy on Wednesday/Thursday of the same week depending on the desired dose. The patients will be then transferred to nuclear medicine department for planar and SPECT/CT bremsstrahlung imaging of the chest and abdomen on the same day.

E. Low-dose Y90 Planar and SPECT/CT of chest and abdomen (Monday)

Quantitative reconstruction of Y90 bremsstrahlung SPECT/CT will follow the procedures outlined by Siman et al[41]. When low dose Y90 bremsstrahlung follows administration of Tc-99m on the same day, the procedures of Siman et al have to be adapted by choosing an energy window for the bremsstrahlung imaging with a minimum energy of 160 keV, avoiding contamination of the image by Tc-99m 140 keV photons. Calibration of the quantitation method for the adapted energy windows is accomplished through comparison of the images of Y90 bremsstrahlung obtained with the standard and adapted energy windows[41].

Please note that this is commonly performed at Emory for our out of town or international patients in whom both mapping and Y90 therapy is performed on the same day. Since only the proportion of activity in each compartment (i.e. tumor, liver and lung) are needed to calculate dose delivered in the setting of known administered activity, filter any energy less than 160 keV will result in accurate quantification of Y90 dose delivered. **Additionally, patient will undergo PET/CT on the same day using a state-of-the-art PET scanner which will only detect Y90 activity without any noise from MAA. This will be used as an additional step to confirm our hypothesis that same MAA and Y90 is feasible.**

The patient will then be discharged from IR after removal of the radial sheath according to our standard protocol.

F. Low-dose Y90 PET/CT of chest and abdomen (Monday)

The patient will then undergo time of flight Y90 PET/CT with one or two bed positions depending on the patient's size. This will also occur on the same day and at the same location as the remainder of mapping day either at EUH or EUHM.

Schedule of Mapping Days:

7:30 AM-9:30 AM: 1st Angiographic study for mapping and MAA delivery

10:00 AM-11:00 AM: MAA SPECT/CT (Patient will go to nuclear medicine with radial/femoral arterial access sheath in place)

11:30 AM-1:00 PM: 2nd Angiographic study for low-dose Y90 delivery (After the procedure, patient's femoral sheath will be removed and hemostasis will be achieved with manual compression or closure device. If procedure performed via radial access, which is more commonly performed currently at Emory, the radial sheath will stay in and removed according to IR protocol after Y90 SPECT/CT.)

2:00 PM-3:00 PM: Y90 Bremsstrahlung SPECT/CT

3:00 PM-3:30 PM: Removal of the radial sheath at IR post procedural area and discharge.

4:30-5:30 PM: Y90 PET/CT.

Patient is free to go home after this.

G. Prospective Personalized Targeted Therapeutic Y90 Tumor(s) Dosimetry (Tuesday/Wednesday)

The required therapeutic Y90 dose will be calculated using MAA SPECT, Y90 SPECT and Y90 PET. **Although all 3 sets of calculations will be made prospectively, the activity calculation based on MAA SPECT (the standard of care) will be used for actual treatment planning.** The activities calculated using Y90 SPECT and PET will be used for post-hoc analysis. Partition model to achieve cytotoxic Target Tumor Dose of >100 Gy will be utilized using the following formulas[7]:

- i. **Desired Tumor Activity (GBq) = (100 Gy X Tumor Mass (Kg)) / 50**
- ii. **Targeted Normal Liver Activity (GBq) = Desired Tumor Activity (GBq) / TNR**
- iii. **Targeted Liver Lobe Activity (GBq) = (Targeted Normal Liver Activity + Desired Tumor Activity) (GBq)**
- iv. **Targeted Liver Lobe Dose (Gy) = Targeted Liver Dose Activity (GBq) X 50 / Liver mass (Kg)**

The liver and tumor mass will be determined using the volumes calculated by MIM software and assuming density of 1.03 g/cm³^[39]. It will be ensured that targeted liver dose remains below 50 Gy which has been shown to be safe with no sequela of radiation induced liver disease while ensuring the target tumor dose >100 Gy[7, 26].

v. **Y90 Activity for administration (GBq) = Targeted Liver Lobe Activity (GBq) X (1+LSF)**

Lung dose after therapeutic Y90 RE will be calculated using the following formula:

vi. **Lung Dose (Gy) = Y90 Activity to be Administered (GBq) X LSF X 50 / Mass of Lungs (Kg)**

Lung Dose <30Gy will be ensured by reducing administered activity if needed (lung mass assumed at 1 Kg)[8].

H. 3rd Angiography and Administration of Y90 Therapy Dose (Wednesday/Thursday)

The actual prescribed Y90 activity as calculated above using MAA SPECT (**the current standard of care**) will be administered on Wednesday or Thursday of the same week after the shunt study. The desired activity will be drawn from the remainder of activity in the 5-day flex resin microsphere vial. It will be administered by [name] using the same catheter techniques described above. **After the procedure, patient's femoral sheath will be removed and hemostasis will be achieved with manual compression or closure device. If procedure performed via radial access, which is more commonly performed currently at Emory, the radial sheath will stay in and removed according to IR protocol after Y90 SPECT/CT.** The patient will be then transported to nuclear medicine department of Y90 SPECT/CT.

I. Therapeutic-dose Y90 Planar and SPECT/CT (Wednesday/Thursday)

Using the same technique described above (section E), planar and SPECT/CT will be performed using medium energy filter. The patient will then be discharged from IR after removal of the radial sheath according to our standard protocol.

J. Therapeutic-dose Y90 PET/CT of chest and abdomen (Wednesday/Thursday)

The patient will then undergo time of flight Y90 PET/CT with one or two bed positions depending on the patient's size. This will also occur on the same day and at the same location as the remainder of mapping day either at EUH or EUHM.

Below is the conservative estimated timeline of Mapping/shunt studies performed on Wednesday or Thursday:

11:00 AM-12:30 PM: 3rd angiographic study to deliver therapeutic dose of Y90.

1:00 PM-2:00 PM: Y90 Bremsstrahlung SPECT/CT (After the procedure, patient's femoral sheath will be removed and hemostasis will be achieved with manual compression or closure device. If procedure performed via radial access, which is more commonly performed currently at Emory, the radial sheath will stay in and removed according to IR protocol after Y90 SPECT/CT.)

3:00 PM-3:30 PM: Removal of the radial sheath at IR post procedural area and discharge.

4:30-5:30 PM: Y90 PET/CT at Cardiac PET center on the 4th floor of EUHM.

Patient is free to go home after this.

K. Y90 Therapy Tumor, Liver, and Lung Dose Calculation (Friday)

Utilizing the MIM software, post Y90 therapy PET/CT data and partition method described above, the mean actual dose delivered to the tumor, normal liver, and lung will be calculated by Drs. [name] and [name]. The software will generate ROIs from the inside to the periphery of the tumor based on Y90 delivery, and Dose Volume Histograms (DVH) plotting the delivered dose as a function of liver volume. Using DVH, % of tumor volume receiving >100Gy and dose range to the tumor will be also calculated.

L. Follow-up phone call [REDACTED] or study nurse (1-week post therapy)

Patient will be followed by phone to ensure they are doing well, and they will be screened for any symptoms related to adverse events. If any concerning symptoms is reported, they will be brought to IR clinic for further evaluation.

M. 1-Month clinical and Imaging Follow-up

- Multiphase liver mass protocol MRI or CT will be obtained
- Brief medical history
- Symptom-directed physical exam
- ECOG Performance Status
- Vitals signs
- Review of prior/concomitant medications
- Clinical laboratory tests for:
 - Hematology
 - CMP

N. 3-Month clinical and Imaging Follow-up

- Multiphase liver mass protocol MRI or CT will be obtained
- Brief medical history
- Symptom-directed physical exam
- ECOG Performance Status
- Vitals signs
- Review of prior/concomitant medications
- Clinical laboratory tests for:
 - Hematology
 - CMP

O. 6-Month clinical and Imaging Follow-up

- Multiphase liver mass protocol MRI or CT will be obtained
- Brief medical history
- Symptom-directed physical exam
- ECOG Performance Status

- Vitals signs
- Review of prior/concomitant medications
- Clinical laboratory tests for:
 - Hematology
 - CMP

End of Treatment

End of treatment is defined as the last planned Y90 therapy within the 6-month dosing period. For subjects who discontinue drug treatment prior to 6 months, end of treatment is considered the last visit where the decision is made to discontinue treatment. All required procedures may be completed within \pm 7 days of the end of treatment visit. Repeat disease assessment is not required if performed within 28 days prior to the end of treatment visit.

Assessments for subjects who have completed treatment and achieved disease control, or have discontinued treatment due to toxicity in the absence of confirmed progressive disease are provided in the Schedule of Event.

All subjects will be followed for survival until the end of the study regardless of further treatments, or until the sponsor ends the study.

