2.2.2 Correlative Studies Background

An anthropomorphic torso phantom with lung and liver compartments (Data Spectrum Corporation, Durham, North Carolina) was used to assess low-dose imaging capabilities with Y90 (**Figure 1**). Initially, 10.9 mCi of liquid Y90 HCL was injected into the liver compartment with an additional 2.9 mCi in two fillable spheres mounted in the liver to simulate liver tumors. Total liver activity was 13.8 mCi. Lung compartments were filled with a mixture of Styrofoam beads and a Y90 HCL solution with a total activity of 1.12 mCi. **This gave a true LSF of 7.5% and a TNR of 10.** The phantom was imaged using our planar imaging protocol for shunt calculations and with our SPECT/CT protocol for Y90. Energy windows were chosen for quantitative Y90 Bremsstrahlung imaging. Planar imaging (as clinically used for the MAA shunt studies) yielded 6.4% LSF. On the other hand, SPECT calculation of the lung shunt was 6.9%.

SPECT/CT depicted the distribution of activity in the phantom and gave TNR of 6. The PET/CT images on the other hand had very few counts in both the liver and lungs due to the small number of positron emissions by low-dose Y90. Nevertheless, the TNR measured by PET was very accurate at 10 and the LSF was measured at 4.9%. **As depicted by our phantom study results, each imaging modality in the setting of low-dose Y90 have advantages and disadvantages. While PET appears to be accurately measuring TNR, Bremsstrahlung SPECT appears to be more accurate in estimating LSF. Our goal through the proposed study is to ultimately optimize and validate low-dose Y90 PET and/or SPECT as the single study needed to accurately plan Y90 therapy based on institutional availability.**

[figure not shown]

Figure 1 shows images used in the phantom analysis: A) Planar (static image), B) SPECT coronal, C) CT coronal, D) PET coronal.

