7.2.4 Preparation

Each hot lab at EUH or EUHM have their own ⁹⁹Tc generator which will be labelled with MAA according to standard clinical protocol used on a daily basis.

15 mCi of Y90 will be drawn from the 196 mCi vial on Monday to use for the mapping study. The remainder of the 181 mCi activity will decay to 83 mCi by Thursday (Y90 half-life = 64.1 hours). The mother vial will be stored in a clean secure place in hot lab with sterile alcohol swab or paraffin placed on the diaphragm of the vial. After prospective therapeutic dose calculation detailed above, the appropriate activity will be drawn from the mother vial.

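### Delivered lung dose rests on PET/CT alone, the modality the plan's own phantom found least accurate for LSF, and the post-therapy image still contains the low-dose Y90 that is being judged

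*Combined protocol and SAP*

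**What the plan says.** The primary objective (section 3) is to compare low-dose Y90 with MAA as predictors of the dose actually delivered to tumor, liver and lung. Section 4.1 sets the delivered dose against both predictions. Step K of section 8.1 defines the delivered dose. Its source is given as "Utilizing the MIM software, post Y90 therapy PET/CT data and partition method described above". Its scope takes in all three organs: "the mean actual dose delivered to the tumor, normal liver, and lung will be calculated". Step I of the same section acquires post-therapy planar and SPECT/CT images, but step K does not use them.

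Section 2.2.2 reports a phantom imaged at low-dose activity. "Total liver activity was 13.8 mCi", and the lung compartments were filled "with a total activity of 1.12 mCi". The stated result is: "This gave a true LSF of 7.5% and a TNR of 10". On LSF, "Planar imaging (as clinically used for the MAA shunt studies) yielded 6.4% LSF"; SPECT gave 6.9% and PET 4.9%. On TNR, PET gave 10 and SPECT 6. The section concludes that PET measures TNR accurately, while "Bremsstrahlung SPECT appears to be more accurate in estimating LSF".

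On the low dose itself, section 7.2.4 says: "15 mCi of Y90 will be drawn from the 196 mCi vial on Monday to use for the mapping study". The therapeutic activity is drawn from the same vial and given on Wednesday or Thursday of that week. The plan does not describe removing the first activity from the post-therapy image.

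**The concern.** The delivered dose is the yardstick for both predictors, so an error in it can decide which one looks better. For lung, the plan chose the modality that its own phantom ranked last and gave no lung-specific reason. Low-dose PET is also one of the predictors, so a PET under-reading that persists at therapeutic activity would be common to predictor and reference, and MAA would be charged with the difference.

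The second problem does not depend on the phantom. Microspheres given on Monday are still decaying in the patient at the therapy scan. The reference image is therefore a mixture of the therapy distribution and the low-dose distribution, so one predictor forms part of its own reference. This applies to tumor and liver as well as lung.

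**Working it through.** **Phantom truth.** Lung activity over total activity: 1.12 / (1.12 + 13.8) = 1.12 / 14.92 = 7.51%. The plan's 7.5% reproduces.

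**Error by modality (reading / 7.5 - 1).**
- SPECT: 6.9 / 7.5 - 1 = -8.0%
- Planar: 6.4 / 7.5 - 1 = -14.7%
- PET: 4.9 / 7.5 - 1 = -34.7%

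**Effect on the reference.** In section 7.1.2 lung dose is activity x LSF x 50 / lung mass. For a given activity and lung mass, a relative error in LSF becomes the same relative error in lung dose. Let f be the share of the phantom PET error that persists at therapeutic activity. The documents give no value, so f runs from 0 to 1 as an assumption. The reference then reads 7.5 - f x (7.5 - 4.9), and the apparent error of a predictor is its value over the reference, minus 1.

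| f | Reference LSF (%) | Accurate predictor (7.5) | Low-dose SPECT (6.9) | Low-dose PET (4.9) |
|---|---|---|---|---|
| 0 | 7.50 | 0% | -8.0% | -34.7% |
| 0.25 | 6.85 | +9.5% | +0.7% | -28.5% |
| 0.5 | 6.20 | +21.0% | +11.3% | -21.0% |
| 0.75 | 5.55 | +35.1% | +24.3% | -11.7% |
| 1 | 4.90 | +53.1% | +40.8% | 0% |

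An accurate predictor misses the reference by 2.6f points and low-dose PET by 2.6(1 - f), so low-dose PET is closer only when f exceeds 0.5. If SPECT were the reference and kept its full phantom error, an accurate predictor would appear to over-predict by 7.5 / 6.9 - 1 = 8.7%.

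**Residual low dose.** The plan's decay figure reproduces: 181 x 2^(-72/64.1) = 83.1 mCi, against 83 stated. The same factor gives 15 x 2^(-72/64.1) = 6.89 mCi, or 0.255 GBq at 0.037 GBq per mCi, on Thursday. This assumes that the microspheres stay where they lodge.
- Whole vial given: both portions decay together, so the residual share is w = 15 / 196 = 7.7%. This is the minimum.
- Assumed 3 GBq therapy: 0.255 / 3.255 = 8%.
- Assumed 1 GBq therapy: 0.255 / 1.255 = 20%.

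With T the therapy LSF, L the low-dose LSF and A the MAA LSF, the image shows M = (1 - w)T + wL.
- Low-dose error: L - M = (1 - w)(L - T), always smaller by the share w.
- MAA error: A - M = (A - T) - w(L - T), which can move either way.

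**The case against.** A reader might infer that low-dose PET and therapy PET will agree whatever the truth, and that MAA is bound to look like an over-predictor. The documents do not support that. The phantom was imaged only at about 15 mCi, and section 2.2.2 links the sparse PET counts to the low dose. Up to 83 mCi remains for therapy, about 5.6 times as much (83 / 14.92), so the error may shrink. If it vanishes, low-dose PET looks worst and an accurate MAA shows no error. The phantom also gives one reading per modality with no measure of uncertainty, so 4.9% could be partly noise, and noise would not be shared between two scans. These points stand and make the direction conditional.

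They do not make persistence implausible, because 83 mCi is a ceiling. As an illustration, take one spherical 7 cm lesion (the size limit in section 5.1) at 1.03 g/cm³, which weighs 0.185 kg. With exactly 100 Gy and the TNR of 5.4 and LSF of 11.66% from section 10.2, the printed formulas give 100 x 0.185 / 50 = 0.37 GBq to tumor. Then 0.37 x (1 + 1/5.4) x 1.1166 = 0.49 GBq, or about 13 mCi, which is close to the phantom's activity. The plan aims above 100 Gy, so actual activities may be higher.

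A reader might also infer that the primary test is biased by step K. It is not: section 10.3 compares MAA with Y90 LSF and TNR directly and does not use the delivered dose.

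The plan does have reasons for PET. Section 2.1 treats post-therapy PET/CT as the accepted standard, and the phantom TNR supports PET for tumor and liver. Section 3 also foresees optimising both modalities at therapeutic dose, but it commits to no SPECT lung dose. Finally, the residual is dose that the patient really received, so whether delivered dose includes it is partly a matter of definition. The plan has not stated that definition, and leaving the residual in favours one of the two predictors.

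**Conclusion.** The concern holds in conditional form. Delivered lung dose rests on PET/CT only, against the plan's own phantom ranking for LSF and without evidence at therapeutic activity. The resulting apparent over-prediction by an accurate MAA lies between 0 and 53%, depending on an unknown carry-over. Low-dose PET gains over an accurate MAA only if more than half of the error persists. Neither a fixed bias toward the hypothesis nor any harm to the section 10.3 test follows from step K.

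The residual low dose is the firmer part. It makes up at least 7.7% of imaged activity, and about 20% for an assumed 1 GBq therapy on Thursday. It shrinks the low-dose LSF discrepancy by that share, with no matching benefit to MAA. What is at stake is the delivered-versus-predicted comparison named in the primary objective, so this should be settled before analysis.

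**What to change.** In step K, also compute and report delivered LSF and lung dose from the post-therapy SPECT/CT already acquired. Keep PET for tumor and liver. State whether the lung conclusion is the same on both modalities. Requiring it to hold on both would be a preference and not a necessity, since SPECT LSF is also untested at therapeutic activity in these documents.

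Define whether delivered dose includes the low-dose administration. Before comparing delivered with predicted dose, subtract the decay-corrected low-dose activity compartment by compartment, using the low-dose image of the same modality as the post-therapy image. Report results with and without the subtraction.

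The cost is analysis work, because all the scans are already planned. The downside is some added noise from subtracting a low-count image, which is why both sets of results should be shown.

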4. STUDY DESIGN

4.1 Overall Design

This study is a single arm phase II prospective clinical trial in which patients with HCC who are deemed suitable for Y90 radioembolization will be recruited. Patients will undergo standard of care mapping study with ^{99}Tc -MAA to plan for Y90 radioembolization therapy. The additional, non-standard of care, intervention will be to do a second mapping study using low-dose Y90 (15 mCi) before the therapeutic Y90 radioembolization.

The distribution of MAA in terms of lung shunt fraction (LSF) and tumor to normal liver activity ration (TNR) will be compared to that of low-dose Y90. The treatment planning will be performed using standard of care MAA biodistribution using partition dosimetry model.

After administration of therapeutic Y90 dose, the actual dose delivered to tumor, non-tumoral liver (NTL) and lungs will be compared to the dose predicted by MAA and low-dose Y90.

The patients will be followed-up clinically and with imaging at 1, 3 and 6 months to determine tumor response, potential treatment related toxicity and to determine TDRT.

Hypothesis: Low dose Y90 microspheres as the treatment planning radiotracer will allow more accurate prediction of therapeutic Y90 liver biodistribution, which will enable us to perform prospective personalized dosimetry for every individual patient.

The results of this study will determine the safety and efficacy of using low dose Y90 as a direct surrogate for treatment planning to ensure delivering cytotoxic Y90 dose to the targeted tumor(s), while concomitantly minimizing liver and lung toxicity with more accurate prediction of therapeutic Y90 biodistribution. **Our long-term objective is to increase the likelihood of objective tumor response, prolonged progression-free survival (PFS) and overall survival (OS) in patients with HCC treated with Y90 RE.**

The study is a single-arm in study in which each patient will undergo two sets of mapping procedure before the actual Y90 therapy. One with standard of care ^{99}Tc -MAA and one with low-dose (15 mCi) Y90 microspheres. **Therefore, the additional intervention in the study is the second mapping procedure with low-dose Y90 microspheres.** Each patient will be used as their internal control to minimize selection biases. **Additional to standard of care Y90 SPECT/CT after therapy, the patient will undergo one PET/CT after low-dose Y90 and one PET/CT after Y90 therapy.**

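### The post-therapy PET that defines actual dose still holds at least about 7.7% planning-dose Y90, and no step accounts for it in the accuracy comparison or in TDRT

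*Combined protocol and SAP*

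**What the plan says.** - **Planning dose, Monday (8.1 D).** "Fifteen (15) mCi of resin microsphere will be drawn from a 5-day flex dose vial containing approximately 196 mCi of activity". It goes into the branches already used for MAA: "From this location, 15 mCi of resin Y90 microspheres will be administered".
- **Therapy (8.1 H).** The prescribed activity "will be administered on Wednesday or Thursday of the same week after the shunt study", by the same catheter technique. "The desired activity will be drawn from the remainder of activity in the 5-day flex resin microsphere vial". Section 7.2.4 gives the decay: "The remainder of the 181 mCi activity will decay to 83 mCi by Thursday (Y90 half-life = 64.1 hours".
- **Actual dose (8.1 J and K).** A PET/CT on the day of therapy supplies the mean dose per compartment: "post Y90 therapy PET/CT data and partition method described above, the mean actual dose delivered to the tumor, normal liver, and lung". The same step produces dose-volume histograms and the share of tumor volume above 100 Gy.
- **Use of that dose.** Section 4.1 states that "the actual dose delivered to tumor, non-tumoral liver (NTL) and lungs will be compared to the dose predicted by MAA and low-dose Y90". Section 3 sets the same comparison as the primary objective. Sections 10.4 and 10.5.4 relate tumor dose to response (TDRT, percent volume above 100 Gy, LD 50 and LD 70).
- **Quantification.** For low-dose SPECT, 8.1 E relies on compartment shares: "proportion of activity in each compartment (i.e. tumor, liver and lung) are needed to calculate dose delivered in the setting of known administered activity". For PET, 8.1 K names the partition method but does not say whether activity is measured absolutely.
- **Carry-over.** Section 8.1 E keeps Tc-99m out of the Y90 SPECT with a 160 keV window. Sections 8, 8.1, 10.4 and 10.5.4 say nothing about Monday's Y90 in the post-therapy scan.

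**The concern.** An energy window can separate Tc-99m from Y90, but nothing in the image separates Monday's Y90 from Thursday's. Following 8.1 K as written therefore gives an actual dose that mixes the therapeutic deposit with what is left of the planning deposit. Low-dose Y90 is then judged against a reference that it partly supplies; MAA is not.

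Two results depend on this scan. The first is the comparison of delivered with predicted dose, which the primary objective promises. The second is the dose-response work: tumor response follows both deposits, but the only delivered tumor dose that the plan calculates comes from the therapy scan. A threshold that leaves out contributing dose reads too low for patients who receive no Y90 planning injection.

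**Working it through.** **Plan's own figure.** 181 × 2^(−72/64.1) = 83.1 mCi, against 83 in 7.2.4. It reproduces. The Wednesday equivalent (48 h) is 107.7 mCi.

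**Residual at the PET.** Using mid-times from the timetable, Monday 12:15 to 17:00 on the therapy day is 76.75 h (Thursday) or 52.75 h (Wednesday). 15 × 2^(−t/64.1) gives 6.5 or 8.5 mCi.

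**Residual share w of imaged activity.** Both doses come from one vial and decay together, so the floor is 15/196 = 7.7% on either day, reached when the whole remainder is given. Otherwise, for therapeutic activity A imaged 5.25 h later, w = residual / (residual + A × 2^(−5.25/64.1)).

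| A (mCi) | Thursday | Wednesday |
|---|---|---|
| 40 (assumed) | 15% | 18% |
| 20 (assumed) | 26% | 31% |

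The assumed activities are illustrative. A 7 cm sphere at 1.03 g/cm³ weighs 0.185 kg. With 100 Gy, TNR 5.4, LSF 11.66% and an assumed N = 0.5–1.0 kg of normal liver, (100 × mass/50 + (100/5.4) × N/50) × 1.1166 GBq is 17–22 mCi for one such lesion and 39–45 mCi for three. The printed formula for normal-liver activity has no liver-mass term; used as printed, it gives 13 and 40 mCi. The target is above 100 Gy, so real activities may be higher.

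**Direction.** Let S, M and T be the low-dose, MAA and true therapeutic values.

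- Proportion reading: reference = (1−w)T + wS.
- Absolute reading: reference = T + rS, with r = 15/181 = 0.083 at the floor. Both predictions use therapeutic activity only.

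Proportion reading for LSF at the floor, with M = 11.66 and S = 5.83 (section 10.2) and T assumed:

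| T | Reference | Low-dose absolute error | MAA absolute error |
|---|---|---|---|
| 4.0 | 4.14 | 1.83 → 1.69 | 7.66 → 7.52 |
| 5.83 | 5.83 | 0 → 0 | 5.83 → 5.83 |
| 8.0 | 7.83 | 2.17 → 2.00 | 3.66 → 3.83 |
| 11.66 | 11.21 | 5.83 → 5.38 | 0 → 0.45 |
| 14.0 | 13.38 | 8.17 → 7.54 | 2.34 → 1.71 |

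The gap between tracers moves toward low-dose Y90 when T lies between the predictions. It does not move when T lies beyond the low-dose value, and there is no bias when T = S. Beyond MAA's value, absolute errors tilt only while the pulled reference crosses MAA's value (at 14.0 the gap stays 5.83); squared errors still tilt toward low-dose Y90.

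**All compartments at the floor.** Errors are low-dose / MAA, in percentage points of therapeutic activity. Tumor share = (1−LSF) × TNR × 0.185 / (TNR × 0.185 + 1.0), with 1.0 kg of normal liver assumed. TNR is 5.4 for MAA and 5.4/0.7 = 7.71 for low-dose Y90. Tumor shares are 44.1 (MAA) and 55.4 (low-dose); liver shares are 44.2 and 38.8.

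| Compartment, truth placed | Uncontaminated | Proportion | Absolute |
|---|---|---|---|
| Lung, midway | −2.9 / +2.9 | −2.7 / +3.1 | −3.4 / +2.4 |
| Lung, at low-dose | 0 / +5.8 | 0 / +5.8 | −0.5 / +5.3 |
| Tumor, midway | +5.6 / −5.6 | +5.2 / −6.0 | +1.0 / −10.2 |
| Tumor, at low-dose | 0 / −11.2 | 0 / −11.2 | −4.6 / −15.8 |
| Liver, midway | −2.7 / +2.7 | −2.5 / +2.9 | −5.9 / −0.5 |
| Liver, at low-dose | 0 / +5.4 | 0 / +5.4 | −3.2 / +2.2 |

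**Error rates, proportion reading.** The plan names no test for this comparison, so I assumed a paired t-test of absolute errors: n=30, equally accurate tracers, zero-mean errors, nominal 2.5% per side, 20,000 simulated trials. With biodistribution error b and measurement error m:

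- Uncorrected: low-dose (1−w)b_S + m_S; MAA b_M + m_M − w·b_S.
- Subtracted: low-dose b_S + m_S/(1−w); MAA b_M + m_M + [w/(1−w)]·m_S.

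| Error structure | Uncorrected: false low-dose better (w = 0.077 / 0.15 / 0.26) | Subtracted: false low-dose worse |
|---|---|---|
| No m, correlation 0 | 6 / 13 / 36% | about 2.5% |
| Half m, correlation 0 | 4 / 6 / 11% | 4 / 6 / 10% |
| Half m, correlation 0.5 | 3 / 4 / 6% | 4 / 6 / 11% |

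**Planning deposit missing from TDRT, as a share of total activity.**

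- Proportion reading, 15/(15+A): 15%, 27% and 43% at 83, 40 and 20 mCi; 12% at 107.7 mCi.
- Absolute reading, (15−R)/(15+A), where R is the planning activity left at therapy (6.9 mCi Thursday, 8.9 Wednesday): 8%, 15% and 23% on Thursday at 83, 40 and 20 mCi; 5% on Wednesday at 107.7 mCi.

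**The case against.** The partition method named in 8.1 K works from ratios, which agrees with 8.1 E, so the proportion reading is the better supported one for mean dose. On that reading the bias is zero if planning and therapeutic Y90 distribute identically, and sections 2.1 and 4.2 call the low-dose microspheres bioidentical. Section 10.2 takes low-dose LSF as half of MAA's because MAA overestimates true Y90 LSF, which puts the truth at the low-dose value rather than midway. All of this stands. It limits direction and size but does not remove the fault, because identical distribution is what the comparison is meant to test. Absolute quantification also remains possible for the dose-volume histograms.

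A reader might infer that the accuracy comparison is rigged for low-dose Y90. The documents do not support that: the tilt depends on where the truth lies, and on the absolute reading it can run against low-dose Y90. The 36% false-positive rate needs no measurement error, independent errors and w = 0.26, whereas the phantom PET in 2.2.2 read an LSF of 4.9% against a true 7.5%.

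A reader might also infer that the subtracted reference should be the main analysis. With half the variance from measurement error and correlation 0.5, subtraction errs more often against low-dose Y90 than the uncorrected reference errs in its favor.

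Finally, the TDRT definition in 10.5.4 excludes nothing in words. The omission arises because 8.1 K offers only the therapy scan.

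**Conclusion.** The concern holds as a fault in how the reference and the TDRT dose are constructed, and it goes beyond a missing detail. Between 6.5 and 8.5 mCi of planning Y90 is present at the post-therapy PET, at least 7.7% of imaged activity, and the available text neither subtracts nor adds it. The floor assumes that the full 15 mCi reaches the patient and that the vial, given as approximately 196 mCi, holds that amount.

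For the accuracy comparison the effect is modest on the proportion reading. With truth midway, lung errors move about 0.2 percentage points at the floor, and false findings for low-dose Y90 are about 3–6% against a nominal 2.5% (half measurement error, correlation 0.5, under a test that the plan does not state). On the absolute reading, direction and size differ by compartment and by where the truth lies.

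For TDRT the omission is more certain. The planning deposit is left out wholly (12–43% of total activity) or partly (5–23%). These are shares of activity, and equal shares of tumor dose only if both injections distribute alike.

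It would be wrong to extend this to the formal primary tests: the paired comparisons of LSF and TNR in 10.3, and n=30, do not use the post-therapy scan.

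**What to change.** 1. In 8.1 K, 10.4 and 10.5.4, define the dose for TDRT, percent tumor volume above 100 Gy, and LD 50 and LD 70 as planning plus therapeutic deposits, with the residual counted once. State in 8.1 K whether PET is quantified absolutely or as proportions times administered activity.
2. For the accuracy comparison, report w for each patient and give two results side by side without ranking them: one with the uncorrected reference, one with the registered low-dose scan, decayed to the post-therapy scan time, subtracted. Claim better accuracy for either tracer only if the two agree.

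Both scans are already scheduled, so the cost is image processing and wording. The drawback is noise and registration error from subtracting a low-count scan, which works against low-dose Y90; the plan should say so.
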